## 12 Sample size determination

In this trial, propranolol was used as the control group to evaluate the efficacy and safety of the atenolol group (experimental group). The treatment response after 6 months of medication was used as the key therapeutic index. To calculate the sample size for this trial, we used the following assumptions:

- (1) A 2-sided 0.05 significance level;
- (2) Ratio of the propranolol group: atenolol group = 1:1;
- (3) A statistical power of 90%;
- (4) A 20% dropout rate due to ineligibility;
- (5) A follow-up of at least 96 weeks;
- (6) A 24-month recruitment period; and
- (7) In this trial, the atenolol group's evaluation variables were compared with the propranolol group's evaluation variables to test for noninferiority. The hypotheses are listed below:

-H0: Twenty-four weeks after therapy initiation, compared to the treatment response of propranolol therapy, that of atenolol was inferior; and

-H1: Twenty-four weeks after therapy initiation, compared to the treatment response of propranolol therapy, that of atenolol was non-inferior.

(8) Very limited data are available in the literature that can be used to set hypotheses for atenolol treatment. Existing case studies are mainly based on small single-center experiences. According to previous studies, propranolol's total treatment response is assumed to be 70-100%, and atenolol's total treatment response is assumed to be 70-100%. In addition, assuming that the atenolol on propranolol response rate does not fall by greater than 15%, the noninferiority margin was selected to be -15%.

(9) Assuming the ulceration rate in both groups to be 10%.

(10) A sample size of 180 patients was determined to be required for each group (a total of 360 patients).

[figure not shown]
[figure not shown]
---

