## **18 Collection and assessment of series of digital photographs**

Digital photographs of each target hemangioma were acquired by the site investigators at baseline and at 1, 4, 12, 24 and 96 weeks after treatment. The detailed procedures are listed below:

(1) The investigators used a unified camera model. The acquisition procedures ensured consistency in lighting, exposure and distance from the camera. All digital photographs were obtained using digital single-lens reflex cameras (Nikon D7000 or Nikon D7100, Nikon Inc., Melville, NY).

(2) For each participant site, the series images were taken in the same room. The room was a naturally well-lit room. The acquisition of digital photographs was performed carefully to avoid glare and direct light deep into the room.

(3) The background behind the patient when the images are acquired was either the parent's (or guardian's) chest or shoulder or an examination couch. The parents and patients wore light-color, nonreflective clothes. Similarly, the examination couch was covered with a light blue, non-reflective bed sheet.

(4) For each patient, at least one photograph (a front-on view with or without side-on view) was taken at each visit. If the patient had a mixed hemangioma, front-on view and side-on view photographs were taken (not mandatory).

(5) The quality of all the photographs was verified by site investigators before they were transferred to the CIS. If the photographs were not compliant with the acquisition protocol, repeated acquisition of the images was immediately performed.

(6) Each photograph was uploaded with the following information: patient ID number and date of photograph acquisition. The central investigators assessed the quality of the digital photograph once more.

(7) Digital photographs were independently assessed by three investigators (research assistants) working in the CIS who were unknown to the study group assignment and blinded to the clinical information. None of these investigators was involved in the clinical management of patients with IH. They were trained specifically to assess hemangioma evolution (response or nonresponse), hemangioma size and hemangioma color using a series of digital photographs.

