## 19 Primary outcome measures

The primary outcome measure was the clinical response at 6 months in the intention-to-treat population. The intention-to-treat population was defined as all patients who had undergone randomization. If after assignment, a patient did not receive a drug administration or if an evaluation was never made after drug administration, the patient was excluded from the intention-to-treat population.

Digital photographs of IHs were independently obtained by three investigators who were unknown to the study group assignment. In the case of multiple IHs, only the most clinically important IH (typically the largest or most ulcerated IH) was documented.

Changes in IH size and color were classified as a complete response, nearly complete response, partial response or no response. The primary outcome measure was any response or nonresponse at 6 months in the intention-to-treat population of all patients who underwent randomization. The any response included compete, nearly complete and good responses; the nonresponse included stable or deteriorated:

-A complete response was defined as no redundant tissue or telangiectasia was identified.

-A nearly complete response was defined as a minimal degree of telangiectasis, erythema and skin thickening.

-A partial response was defined as a size reduction or change in color that did not meet the nearly complete resolution criteria.

-Stable was defined as no changes in size or color between baseline and month 6.

-Deterioration was defined as further growth of the target hemangioma.

Treatment failure was defined as patients withdrawing from trial treatment due to nonresponse and/or severe adverse events.

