**W24**

**W24**

## 20 Secondary outcome measures

### 20.1 Hemangioma Activity Score

The key secondary outcome measure was the Hemangioma Activity Score (HAS), which was measured at baseline and at 1, 4, 12 and 24 weeks using digital photographs. The photographs of the target hemangioma acquired at each visit were sent to the CIS. The consecutive digital photographs were assessed by centralized evaluation at West China Hospital of Sichuan University. Three trained investigators who were unknown to the study group assignments independently evaluated the digital photographs taken at baseline and the follow-up visits. According to previous reports, changes in an individual HAS could be used to evaluate the effect of treatment. Baseline scores were subtracted from posttreatment scores to obtain the change in HAS or the decrease in hemangioma proliferative activity after treatment.

The HAS system has three scoring forms, including the degree of deep swelling, the color of the hemangioma, and the ulceration assessment:

(1) Assessment of the degree of swelling (or protrusion or elevation). A proliferating superficial or mixed IH can present as a protrusion with an overlying red tint. If there is visible swelling (or protrusion or elevation), it was scored as follows:

-Six points if the swelling (or protrusion or elevation) was tense;

-Four points if the swelling (or protrusion or elevation) was 'neutral' (i.e., not tense or less tense) at baseline or had <50% reduction at follow-up;

-Two points when the swelling (or protrusion or elevation) was reduced by 50% or more at follow-up; or

-Zero points when there was no more visible swelling (or protrusion or elevation) at a follow-up.

If the patient had superficial IH and showed no visible evidence of swelling (or protrusion or elevation) at baseline, this step was omitted or we set the point as 0. However, the score for no swelling (which was zero) affected the final score.

(2) Assessment of the color of the IH. The hemangioma color was assessed by blinded central investigators. A bright-red (or shining-red) color suggested that the hemangioma was very actively proliferating. A diminishing red color on the surface was seen during the phases of involution. It is therefore possible that different scores might have been applied to different phases of the same hemangioma. A bright-red hemangioma received the highest score.

---

The intensities of hemangioma color were rated from 5 through 0:

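### The photograph readers are masked to arm but not to time, so doubtful unchanged lesions may be upgraded in both arms, which favours noninferiority; an order-masked reading of the primary pair is a cheap improvement

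*Combined protocol and SAP*

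**What the plan says.** All places are in the combined protocol and SAP.

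- **Masking (Section 18, item 7).** Three independent readers at the central site do not know the treatment group, are blinded to clinical information and take no part in managing the patients. Of their task the item says: "They were trained specifically to assess hemangioma evolution (response or nonresponse), hemangioma size and hemangioma color using a series of digital photographs". Response or nonresponse is the primary endpoint, so reading from a series is not confined to HAS.
- **What travels with the pictures (Section 18, item 6).** "Each photograph was uploaded with the following information: patient ID number and date of photograph acquisition".
- **HAS (Section 20.1).** "The consecutive digital photographs were assessed by centralized evaluation". The swelling item is scored partly by how far swelling has fallen at follow-up.
- **The response boundary (Section 19).** "Stable was defined as no changes in size or color between baseline and month 6". Any size reduction or colour change short of nearly complete resolution is a partial response and counts as any response. No minimum change is set.
- **The test (Section 12).** Noninferiority of atenolol with a margin of −15 percentage points.

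No section says that dates are removed, that order is randomized, or how three discordant reads become one result.

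**The concern.** Masking to arm stops a reader from favouring one drug. It does not stop a reader from favouring the later picture. Both arms receive a beta-blocker, so a reader who knows which picture is week 24 has reason to expect improvement whatever the arm. The line between stable (nonresponse) and partial response is any perceived change, so one doubtful call is enough to move an infant across it.

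Such an error is the same in both arms and pulls the two response rates together. In a superiority trial that would be conservative. Here it makes a truly inferior drug look closer to the control, so it raises the chance of a false noninferiority conclusion.

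**Working it through.** **1. Inputs from Section 12.** "A 2-sided 0.05 significance level", used as the lower limit of a two-sided 95% interval (one-sided 0.025); 90% power; "Ratio of the propranolol group: atenolol group = 1:1"; "A 20% dropout rate due to ineligibility"; margin 15 points; assumed response 70–100% in each arm; 180 per arm. After 20% dropout, 180 × 0.8 = 144 evaluable per arm.

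**2. The plan's own figure.** With equal true rates p, n per arm = (1.960 + 1.282)² × 2p(1 − p) / 0.15².

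- p = 0.80: 149.4, so 150; × 1.2 = 180 (or 150 / 0.8 = 187.5, so 188).
- p = 0.81: 143.7, so 144; / 0.8 = 180.
- p = 0.85: 119.1, so 120; / 0.8 = 150.

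So 180 is compatible with the stated range, but the readable text gives no single planning rate and two figures in that section are not shown. Nothing here counts against 180.

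**3. Effect of equal upgrading.** Let a fraction f of true nonresponders be read as responders in both arms. An observed rate is p + f(1 − p), so the observed difference is (1 − f) × the true difference. With propranolol at 85% and atenolol at 70% (a true deficit exactly at the margin):

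- f = 0.10: 0.85 + 0.10 × 0.15 = 0.865 and 0.70 + 0.10 × 0.30 = 0.730; difference −13.5 points.
- f = 0.20: 0.880 and 0.760; difference −12.0 points.

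**4. False noninferiority rate.** Section 25.3 names no test or interval for the primary comparison, so a Wald interval is assumed. The normal approximation for f = 0.10 and 144 per arm is:

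- SE = √[(0.865 × 0.135 + 0.730 × 0.270) / 144] = 0.0467
- (0.150 − 0.135) / 0.0467 − 1.96 = −1.64, a probability of 5.1%

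Exact enumeration over both binomials gives:

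| f | observed difference | 144 per arm | 180 per arm |
|---|---|---|---|
| 0 | −15.00 | 2.55% | 2.57% |
| 0.05 | −14.25 | 3.66% | 3.85% |
| 0.10 | −13.50 | 5.20% | 5.67% |
| 0.20 | −12.00 | 10.18% | 11.73% |

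**5. Other control rates** (144 per arm, exact, f = 0 then f = 0.10): 70%, 2.5% then 4.5%; 80%, 2.5% then 4.9%; 90%, 2.7% then 5.9%; 95%, 3.1% then 7.3%. The rate roughly doubles at f = 0.10 across the planning range.

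**6. What f consists of.** Visible growth is not easily read as improvement, so f is roughly the share of nonresponders who are stable times the chance that a stable lesion is upgraded. For example, 50% × 20% = 0.10, and 30% × 20% = 0.06 (3.9% false noninferiority with 144 per arm at 85% and 70%). Neither factor is in the documents.

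**The case against.** The best case for the plan is that its reading is already careful. Photography is standardized, and the readers are central, trained, independent, masked to arm and uninvolved in care. Comparison with a known baseline follows from the endpoint definition. All of that stands, and it protects well against bias that differs between arms. It does not address an expectation shared by both arms.

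A reader might infer that the documents have readers looking at dated photographs in chronological order. They do not say so. The date is listed as information uploaded with the file, the reader's display is not described, and the word consecutive comes from the HAS section, a secondary outcome. What the text supports is narrower: order is not hidden by any stated rule, and the definitions imply that the baseline picture is known.

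It is also fair that f is hypothetical and acts only on part of the nonresponders. Eligible lesions are proliferating, so some nonresponders will show clear growth. Infants who need another hemangioma treatment are failures under Section 17.3; if these count as nonresponse, no photograph can upgrade them. Both facts push f down.

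The calculation also leaves out responders misread as stable. This does not rescue the plan: if a fraction g is downgraded equally in both arms, the difference shrinks by (1 − f − g). With a control rate of 80% and 144 per arm, f = 0.20 alone gives 9.1%, and adding g = 0.05 gives 11.2%.

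**Conclusion.** The point holds as a cheap improvement. Time order is not masked, the response boundary has no minimum change, and equal upgrading in both arms favours noninferiority. The direction is clear; the size is not known. At a true deficit of 15 points, small upgrading (f of 0.05 to 0.10) takes the error from about 2.5% to between 3.7% and 5.2% with 144 per arm. Reaching 10% needs f = 0.20, which is less plausible because mainly stable lesions can be upgraded.

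These figures assume a Wald 95% lower limit, true rates of 85% and 70%, the same f in both arms and no downgrading. A reader might take the larger figures as an estimate of this trial's actual error rate. The documents give no misreading rate, so they cannot support that, nor do they show that any lesion was misread.

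**What to change.** Add a paragraph to Section 18 for the primary reading:

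1. Before any HAS reading of that infant, show each reader the baseline and week-24 pictures as an undated pair in random left-right order, framed on the lesion at the same scale. The sequence matters because HAS swelling scoring reveals which picture is baseline.
2. The reader marks which picture is better overall, or no difference, and whether either meets the complete or nearly complete definition. A single overall judgement avoids the conflict of one picture being smaller and the other paler.
3. Lock the reads, then unmask the order. Week 24 better is a response; no difference, or baseline better, is a nonresponse. Take the call of at least two of the three readers.
4. Read HAS afterwards with order known, as now.

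**Cost.** One extra short reading session with the same readers and photographs, a small change to the reading system, and HAS reading held back until the infant's week-24 pair is locked.

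**Limits.** Order can still be guessed from age cues in some infants. False calls of a difference on unchanged pairs become symmetric and fewer, but are not removed: an unchanged pair called different would still count as a response about half the time.

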## 19 Primary outcome measures

The primary outcome measure was the clinical response at 6 months in the intention-to-treat population. The intention-to-treat population was defined as all patients who had undergone randomization. If after assignment, a patient did not receive a drug administration or if an evaluation was never made after drug administration, the patient was excluded from the intention-to-treat population.

Digital photographs of IHs were independently obtained by three investigators who were unknown to the study group assignment. In the case of multiple IHs, only the most clinically important IH (typically the largest or most ulcerated IH) was documented.

Changes in IH size and color were classified as a complete response, nearly complete response, partial response or no response. The primary outcome measure was any response or nonresponse at 6 months in the intention-to-treat population of all patients who underwent randomization. The any response included compete, nearly complete and good responses; the nonresponse included stable or deteriorated:

-A complete response was defined as no redundant tissue or telangiectasia was identified.

-A nearly complete response was defined as a minimal degree of telangiectasis, erythema and skin thickening.

-A partial response was defined as a size reduction or change in color that did not meet the nearly complete resolution criteria.

-Stable was defined as no changes in size or color between baseline and month 6.

-Deterioration was defined as further growth of the target hemangioma.

Treatment failure was defined as patients withdrawing from trial treatment due to nonresponse and/or severe adverse events.

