### ***17.3 Other co-interventions***

In both arms, oral antibiotics (cefaclor suspension), topical ointment antibiotics (mupirocin) and/or wound dressings were permitted to treat ulcerated IH and were recorded. The requirement for any additional IH-specific intervention was considered treatment failure.

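### Section 19 does not assign every lesion to exactly one side of the primary endpoint, and treatment failure is not assigned to nonresponse at week 24

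*Combined protocol and SAP*

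**What the plan says.** Section 19 first gives a four-level scale: "Changes in IH size and color were classified as a complete response, nearly complete response, partial response or no response". It then forms the primary dichotomy: "The any response included compete, nearly complete and good responses; the nonresponse included stable or deteriorated". The term *good* is not defined anywhere; *partial* is.

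The definitions that decide which side a lesion falls on, once it is short of nearly complete, are:

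- Response side: "A partial response was defined as a size reduction or change in color that did not meet the nearly complete resolution criteria".
- Nonresponse side: "Stable was defined as no changes in size or color between baseline and month 6".
- Nonresponse side: "Deterioration was defined as further growth of the target hemangioma".

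Treatment failure appears in two places. Section 17.3 states: "The requirement for any additional IH-specific intervention was considered treatment failure". Section 19 states: "Treatment failure was defined as patients withdrawing from trial treatment due to nonresponse and/or severe adverse events".

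Under Section 18 the endpoint is read from photographs by three investigators at the central site "who were unknown to the study group assignment and blinded to the clinical information". Section 25.3 uses the words success and failure only for missing outcomes, in two opposite extreme-case scenarios.

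**The concern.** A binary primary endpoint needs a rule that puts each patient on one side, and only one. Here partial response is met by either of two limbs, size or colour, while deterioration depends on size alone. When size and colour move in opposite directions, the two definitions can both apply, and they sit on opposite sides of the endpoint. Three readers working independently from the same text could reach different answers without any of them departing from it.

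The second gap concerns patients rather than photographs. A patient whose lesion improved only after another hemangioma treatment was added, or who stopped for lack of effect, would ordinarily count as a nonresponder. The nonresponse list contains only stable and deteriorated lesions, and the readers cannot see who failed treatment.

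The trial tests noninferiority with a margin of -15% (Section 12). In that setting, errors shared by both arms are not automatically conservative, because they can make the arms look more alike.

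**Working it through.** The plan has no figure of its own on this point to reproduce. The check is a logical one, followed by a line of algebra on direction.

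**Step 1. Cross the two attributes.** Take size (smaller, same, larger) by colour (faded, same, redder) for a lesion short of nearly complete response. This gives 3 × 3 = 9 combinations. They are logical cells, not patients. Apply the Section 19 definitions under two readings of colour change: fading only, and any change.

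| Size | Colour | Fading reading | Literal reading |
|---|---|---|---|
| Smaller | Faded | Partial | Partial |
| Smaller | Same | Partial | Partial |
| Smaller | Redder | Partial (size limb) | Partial |
| Same | Faded | Partial | Partial |
| Same | Same | Stable | Stable |
| Same | Redder | **None** | Partial, so a response |
| Larger | Faded | **Partial and deterioration** | **Partial and deterioration** |
| Larger | Same | Deterioration | Deterioration |
| Larger | Redder | Deterioration | **Partial and deterioration** |

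Fading reading: 7 cells have one category, 1 has two and 1 has none (7 + 1 + 1 = 9). Literal reading: 7 cells have one category and 2 have two (7 + 2 = 9), but one of the 7 counts a lesion that only reddened as a response. The larger but faded lesion is double-classified under both readings, so that fault does not depend on how colour change is understood.

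**Step 2. Look for a tie-break.** Section 18 describes reader training and blinding but no order of precedence. Section 19 gives none, and neither does Section 25.3. Section 20.1 associates diminishing red with involution, but it describes the Hemangioma Activity Score, a secondary outcome that is not linked to the primary categories.

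**Step 3. Set the two failure descriptions side by side.**

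| | Section 17.3 | Section 19 |
|---|---|---|
| Trigger | Other hemangioma therapy needed | Withdrawal from trial treatment |
| Reason | Not specified | Nonresponse and/or severe adverse events |
| Week-24 status | Not stated | Not stated |

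A patient who needs added therapy but stays on trial treatment fails under Section 17.3 only. One who withdraws for a severe adverse event with no added therapy fails under Section 19 only. If either is photographed at week 24 and the lesion looks better, the readers will record a response, and no sentence in Section 19 or 25.3 overrides it.

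**Step 4. Direction of a shared error.** Let p be the true response rate in an arm and f the share of true nonresponders scored as responders, equal in both arms. The recorded rate is p + (1 − p)f. Subtracting the propranolol rate from the atenolol rate gives

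(pA − pP) − f(pA − pP) = (pA − pP)(1 − f).

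Any f above zero shrinks the difference toward zero; at f = 0 nothing changes. If f differs by arm, the shift can go either way. The documents give no value for f, so no number is put in.

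**The case against.** **Colour direction is implied.** Partial response sits on a scale of resolution, and Section 20.1 links bright red to proliferation and fading to involution. This stands in large part. A reader might infer that the plan deliberately counts a redder lesion as a response; the documents do not support that as the intended meaning. Even so, the fading reading leaves one cell doubled and one empty.

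**A larger but faded lesion is atypical, and the readers were trained.** Both are fair. Section 19 also refers to example photographs, which are not visible in the text available here. These may reduce inconsistency in practice, but they are not a written rule. Section 10 enrols proliferating lesions at 5 to 20 weeks of age, so growth after baseline cannot be ruled out.

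**Failure naturally means nonresponse, and the two descriptions may be complementary routes to it.** This is plausible for added therapy and for withdrawal due to nonresponse. It remains an inference, and it leaves withdrawal for adverse events open. Nor is reader blinding itself a fault: failure status can be applied at analysis from site records. The plan simply does not say that it will be.

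**Known failures need not be treated as missing.** A reader might infer that Section 25.3 turns a known atenolol failure into a success in the atenolol-favourable scenario. That follows only if a known failure without a week-24 photograph counts as missing data, which Section 25.3 does not say. The scenarios are deliberate extremes, and the opposite one counts missing atenolol outcomes as failures.

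**Conclusion.** The point holds as a fault in the written endpoint rule. The categories are neither mutually exclusive nor, on the more natural reading of colour change, exhaustive. Treatment failure has two different contents and no stated place in the week-24 dichotomy.

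Its size in patients is unknown, because the documents give no frequency for discordant lesions or for treatment failures. A reader might go further and infer a specific inflation of the false noninferiority rate. That is not supported: it would need an assumed misclassification rate, and it would presume that growth overrides fading, a precedence the plan does not state. If the readers had consistently let fading prevail, that would be a different endpoint rather than a misreading.

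What can be said about direction is conditional. A similar rate of scoring nonresponders as responders in both arms favours noninferiority; unequal rates can push either way. Since this is the sole primary endpoint and the remedy is cheap, it should be fixed, but it is not evidence that the trial's conclusion would be wrong.

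**What to change.** In Section 19 and the reader instructions:

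- Replace *good* with *partial* in the any-response list (an editorial slip).
- Define partial response as smaller size or faded colour, without growth, and short of nearly complete.
- State that any growth is deterioration whatever the colour.
- Classify worsening colour without size reduction as nonresponse.

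Applied to the nine cells, this gives 4 partial (three smaller, plus same-size faded), 1 stable and 4 other nonresponse (three larger, plus same-size redder): 4 + 1 + 4 = 9, each with exactly one category.

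In Sections 19 and 25.3:

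- Reconcile the two treatment-failure descriptions.
- State that patients who needed additional hemangioma-specific intervention, or withdrew for nonresponse, before week 24 count as nonresponders. Apply this at analysis from the patient report form (Section 23), so that the readers stay blinded.
- State that these patients are not imputed as successes in either missing-data scenario.
- State how withdrawals for adverse events are scored.

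The cost is wording, with no new assessments. Response rates may be slightly lower, and a faded lesion with some growth will count as nonresponse. Giving growth precedence is a choice that the plan does not make at present, so it should be recorded as one.
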